4.3. Dose Justification

4.3.1. Starting Dose Justification

The starting dose for GSK3368715 has been selected based on preclinical toxicology, pharmacokinetic data from various species and pharmacodynamics (PD) and efficacy data from mouse xenograft tumor models (See IB for the latest information) [GlaxoSmithKline Document Number [2017N334333_02](#)]. In addition, an integrated tumor exposure-PD response model was built to predict efficacious doses.

The Severely Toxic Dose in 10% rats (STD10) as per International Conference on Harmonization (ICH) S9 guidance was 150mg/kg/day for 28 days and the highest non-severely toxic dose (HNSTD) in the dog was 15mg/kg/day for 28 days (GlaxoSmithKline Document Number [2017N334333_02](#)).

Using one tenth of the rat STD10 as per ICH S9 guidance, where STD10 is defined as 150 mg/kg/day administered daily for 4 weeks, translates to 146 mg using the human equivalent dose calculation (60 kg adult with a surface area of 1.62 m²).

Using one sixth of the dog HNSTD as per ICH S9 guidance, where HNSTD is defined as 15 mg/kg/day administered daily for 4 weeks, translates to 81 mg using the human equivalent dose calculation (60 kg adult with a surface area of 1.62 m²).

Minimally anticipated biologic effect level (MABEL): Mouse pre-clinical studies in the Toledo xenograft model revealed that tumor growth inhibition was associated with a minimum 30% increase in MMA in tumor tissues at doses of 10 mg/Kg/Day. Based on this, the MABEL exposures were defined as total AUC (0-24) of 1300 ng·hr/ml (free AUC [0-24] of 500 ng·hr/mL). For prediction of human dose which will reach MABEL exposure levels, the human pharmacokinetic parameters were predicted using preclinical PK IV data (mouse, rat and dog) and scaling to the human time and concentration scale using complex Dedrick plots with correction for maximum lifespan potential ([Boxenbaum, 1983](#)). The predicted human PK parameters are estimated to be 9.6 mL/min/Kg (Clearance), 25 L/Kg (Steady state volume of distribution), 48 hr (Half-Life) and 49% (Bioavailability). Accounting for higher free fraction in human (% unbound 64.2) relative to mouse (% unbound 35.7), projects human equivalent free MABEL exposures to be reached at 62 mg.

Potential therapeutic doses: An integrated tumor exposure-biomarker response model was utilized to describe the relationship between GSK3368715 tumor exposure and MMA increase in Toledo xenograft studies. Based on the model and predicted human PK, a projected human dose of 250 mg QD/110 mg BID will achieve a 95% increase in MMA induction; 99% increase is projected at doses around 900 mg QD and supports escalation upwards of 250 mg QD.

After considering the potential range of starting doses based on toxicology, pharmacology, and xenograft models, the proposed starting dose of 50 mg once daily was selected. Compared with total exposures observed in the most sensitive species, dogs at HNSTD, the starting dose provided 16- fold and 33-fold safety margins for the steady state AUC and C_{max}, respectively.

4.3.2. Dose Justification for Food Effect Sub cohort

Food effect sub-study will be initiated at RP2D with tablets.

Preliminary physiologically based pharmacokinetic (PBPK) modeling suggests that GSK3368715 absorption is not limited by solubility or permeability, and is expected to be not as much affected by food. Further, PBPK modeling to-date and in vitro data from TinyTIM# suggest similar performance between capsules and tablets, and no substantial food effect.

#In-vitro model that mimics dynamic motility, volumes, secretion and digestion in the upper GI tract, designed by TNO/Triskelion [GlaxoSmithKline Document Number [2019N422334_01](#)]

5. STUDY POPULATION

Prospective approval of protocol deviations to recruitment and enrolment criteria, also known as protocol waivers or exemptions, is not permitted. Specific information regarding warnings, precautions, contraindications, AEs, and other pertinent information on the GSK investigational product or other study intervention that may impact participant eligibility is provided in the IBs/IB supplements. Deviations from inclusion and exclusion criteria are not allowed because they can potentially jeopardize the scientific integrity of the study, regulatory acceptability, or participant safety. Therefore, adherence to the criteria as specified in the protocol is essential.

5.1. Inclusion Criteria

Participants are eligible to be included in the study only if all of the following criteria apply:

Age:

1. Participant must be ≥ 18 to years of age inclusive, at the time of signing the informed consent.

Type of Participant and Disease Characteristics

2. Diagnosis of one of the following:

Part 1 (Dose Escalation and food effect cohort):

- Histologically- or cytological-confirmed diagnosis of solid tumor malignancy that is metastatic or non-resectable
- Have received all standard treatment options or are no longer eligible for additional standard treatment options
- Evaluable disease that may be measured directly by the size of the tumor or can be evaluated by other methods.
- Availability of a biopsy of the tumor tissue obtained at any time from the initial diagnosis to study entry. Although a fresh biopsy, which is

obtained during screening, is preferred, archival tumor specimen is acceptable if it is not feasible to obtain a fresh biopsy.

For participants in the PK/PD cohort, a fresh biopsy and consent for one on treatment biopsy are required for enrollment.

Part 2 (Dose Expansion):

• **Cohort 2A & 2B:**

- The availability of archival tumor tissue, or willingness to undergo a fresh biopsy to determine S-methyl-5'-thioadenosine phosphorylase (MTAP) status (any archival tumor specimen must have been obtained within 6 months prior to starting study drug unless approved by the study Medical Monitor). Local MTAP or *CDKN2A* results are acceptable for enrollment but must be confirmed through central laboratory testing.

• **Cohort 2A:**

- Histologically- or cytological-confirmed diagnosis of Diffuse-large B-cell lymphoma (DLBCL)
- Relapse or refractory disease after at least 1 but not more than 4 lines of prior therapy
- At least 1 measurable site of disease according to the Lugano Classification. The site of disease must be greater than 1.5 cm in the long axis regardless of short axis measurement or greater than 1.0 cm in the short axis regardless of long axis measurement, and clearly measurable in 2 perpendicular dimensions.

• **Cohort 2B:**

Pancreatic Cancer

- Histologically or cytologically confirmed adenocarcinoma of the pancreas
- Unresectable, locally advanced (Stage III), or metastatic (Stage IV) disease
- Relapsed or refractory disease after at least 1 prior line of approved, systemic therapy
- At least 1 measurable tumor lesion per RECIST 1.1 ([Appendix 10](#))

Non-small cell lung Cancer (NSCLC)

- Histologically or cytologically confirmed NSCLC
- Stage IV disease
- Tested for presence of EML4-ALK rearrangement
- Received at least 2 prior lines of approved, systemic therapy, of which 1 therapy has to be a platinum containing regimen.

or

Failed a first-line platinum-containing regimen in combination with an anti-PD1 monoclonal antibody and refused a second-line regimen despite being informed about the different therapeutic options and their specific clinical benefit by the investigator; the content of this informed consent discussion including the therapeutic options reviewed by the investigator need to be documented and the participant needs to sign a specific consent form

- At least 1 measurable tumor lesion per RECIST 1.1.

Transitional cell carcinoma of the Urothelium

- Histologically or cytologically confirmed transitional cell carcinoma (TCC) of the urothelium (urinary bladder, urethra, ureter or renal pelvis) including mixed pathology with predominantly (i.e., > 50% of the histopathology sample) TCC with the exception of neuroendocrine or small cell carcinoma
- Unresectable, locally advanced (T4b) or metastatic (lymph node or visceral) disease
- Relapsed or refractory disease after at least 1 prior line of approved systemic therapy
- At least 1 measurable tumor lesion per RECIST 1.1.

3. Adequate organ function as defined by:

System	Laboratory Values
Hematologic	
Absolute neutrophil count (ANC)	$\geq 1.5 \times 10^9/L$
Hemoglobin ^a	Solid malignancy: ≥ 9 g/dL Non-Hodgkin's Lymphoma: ≥ 8 g/dL
Platelets ^a	$\geq 100 \times 10^9/L$
PT/INR and PTT	≤ 1.5 X upper limit of normal (ULN), unless participant is receiving systemic anticoagulation
Hepatic	
Albumin	≥ 2 g/dL
Total bilirubin	≤ 1.5 x ULN NOTE: Isolated bilirubin > 1.5 X ULN is acceptable if: 
 • bilirubin is fractionated and direct bilirubin $< 35\%$ OR • participant has a diagnosis of Gilbert's syndrome
Alanine aminotransferase (ALT)	Part 1 and 2: ≤ 2.5 x ULN Part 2 ONLY: < 5 x ULN is acceptable for participants with documented liver metastases/tumor infiltration
Renal	
Calculated creatinine clearance by Chronic Kidney Disease Epidemiology Collaboration (CKD-EPI) equation or measured from 24hr urine	≥ 50 mL/min

Cardiac	
Ejection fraction	≥Lower limit of normal (LLN) by echocardiogram (minimum of 50%) / MUGA
ECG:QTcF ^b	<450 ms

- a. Participants that require transfusion or initiation of growth factor support in order to achieve necessary platelet and/or hemoglobin must maintain adequate values for at least 7 days without transfusion or while on growth factor in order to be eligible for participation
- b. Baseline QTc interval using Fridericia's formula based on average of triplicate ECGs obtained over a brief recording period.

4. Eastern cooperative oncology group (ECOG) performance status of 0 or 1.

5. Able to swallow and retain orally-administered medication.

Sex

6. **Female Participants:** A female participant is eligible to participate if she is not pregnant or breastfeeding, and at least one of the following conditions applies:

- Is not a woman of childbearing potential (WOCBP)

OR

- Is a WOCBP and using a contraceptive method that is highly effective, with a failure rate of <1%, as described in [Appendix 4](#) during the intervention period and for at least 120 days, corresponding to the time needed to eliminate any study intervention(s) (e.g., 5 terminal half-lives) after the last dose of study intervention. The investigator should evaluate the effectiveness of the contraceptive method in relationship to the first dose of study intervention.

A WOCBP must have a negative highly sensitive pregnancy test (urine as required by local regulations) within 7 days before the first dose of study intervention.

Additional requirements for pregnancy testing during and after study intervention are located in [Appendix 2](#).

The investigator is responsible for review of medical history, menstrual history, and recent sexual activity to decrease the risk for inclusion of a woman with an early undetected pregnancy

Male Participants: Male participants are eligible to participate if they agree to the following during the intervention period and for at least 100 days, corresponding to time needed to eliminate study intervention(s) (e.g., 5 terminal half-lives) plus 90 days after the last dose of study intervention:

Refrain from donating sperm

Plus either:

Be abstinent from heterosexual or homosexual intercourse as their preferred and usual lifestyle (abstinent on a long term and persistent basis) and agree to remain abstinent

OR

Must agree to use contraception/barrier as detailed below

- Agree to use a male condom and should also be advised of the benefit for a female partner to use a highly effective method of contraception as a condom may break or leak when having sexual intercourse with a woman of childbearing potential who is not currently pregnant
- Agree to use male condom when engaging in any activity that allows for passage of ejaculate to another person

Informed consent

7. Capable of giving signed informed consent as described in [Appendix 1](#) which includes compliance with the requirements and restrictions listed in the informed consent form (ICF) and in this protocol.

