Telemetry	X				X								Telemetry only required for doses > 200 mg and must start at least 60 min pre-dose and be continuous for 24h post-dose. See Section 8.2.5.
Holter monitoring	X				X		X		X				Holter monitoring must start at least 60 min pre-dose and be continuous for 24h post-dose.
12-lead ECG (Triplicate)	X	X	X		X		X		X	Q1W	X		On serial PK days (Day 1, 8 and 15), triplicate ECGs will be obtained at or about the time of each PK sample collection, as described in the SRM. On other days, triplicate ECGs will be obtained pre-dose.
Laboratory Assessments (Safety) – perform assessments pre-dose on each dosing day													
Clinical Chemistry, Urinalysis and Coagulations	X				X		X		X	Q1W	X		Refer to Appendix 2 for complete list of required laboratory assessments.
Hematology	X			X	X	X	X		X	Q1W	X		Hematology twice per week for the first two weeks (see Section 2.3.1). Refer to Appendix 2 for complete list of required laboratory assessments.
Pregnancy test					X				X	Q4W	X		Perform only in women of child bearing potential (WOCBP). Pregnancy tests during intervention phase and at discontinuation may be either serum

Procedure	DLT period (Days 1-21) ³								D22 ³	Continuation ³	TDV ¹	Follow-up	Notes		
	D1 ²	D2	D3	D4	D8	D11	D15	D16							
													or urine. Final pregnancy test must be performed within 150 days after last study intervention.		
Study intervention															
Administer study drug	X			←=====Daily Dosing=====→											A dose will be administered on Day 1, no dose will be given on Day 2 or Day 3 of the first cycle, after which, daily dosing will occur through the remainder of cycle 1 and all subsequent cycles. GSK3368715 should be administered in a fasted state at approximately the same time of day (\pm 4 h), with no food for 1 hour before and 2 hours after each dose. See Section 5.3.1 for dosing instructions on serial PK days.
Efficacy Assessment															
Tumor Imaging. Must include CT Chest. Must include CT abdomen if history of documented intraabdominal disease.										Week 9 Day1 then every 8 weeks until Week 33 Day 1 and then Q16W	X		Disease assessments will be performed until disease progression. Participants who discontinue for reasons other than PD will also be followed until the start of subsequent anti-cancer intervention. CR or PR should be confirmed as per response criteria in Appendix 10 .		
Patient Reported Outcomes															

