9.1.2. Dose Expansion

The primary goal of Part 2 is to evaluate clinical activity in each disease specific cohort for GSK3368715 for MTAP- subgroup and MTAP+ subgroup separately.

All evaluations in Part 2 are designed to exclude a 10% response rate representing best available therapy in favour of a 30% response rate.

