I	One node or a group of adjacent nodes	Single extranodal lesions without nodal involvement
II	Two or more nodal groups on the same side of the diaphragm	Stage I or II by nodal extent with limited contiguous extranodal involvement
II bulky ^a	II as above with "bulky" disease	Not applicable
Advanced		
III	Nodes on both sides of the diaphragm; nodes above the diaphragm with spleen involvement	Not applicable
IV	Additional noncontiguous extralymphatic involvement	Not applicable

NOTE. Extent of disease is determined by positron emission tomography–computed tomography for avid lymphomas and computed tomography for nonavid histologies. Tonsils, Waldeyer's ring, and spleen are considered nodal tissue.

a: Whether stage II bulky disease is treated as limited or advanced disease may be determined by histology and a number of prognostic factors.

Criteria for Response Assessment of Non-Hodgkin's Lymphoma

Response	Site	PET-CT-Based Response	CT-Based Response
Complete	Lymph nodes and extralymphatic sites	Complete metabolic response	Complete radiologic response (all of the following)
		Score 1, 2, or 3 ^a with or without a residual mass on 5PS ² It is recognized that in Waldeyer's ring or extranodal sites with high physiologic uptake or with activation within spleen or marrow (eg, with chemotherapy or myeloid colony-stimulating factors), uptake may be greater than normal mediastinum and/or liver. In this circumstance, complete metabolic response may be inferred if uptake at sites of initial involvement is no greater than surrounding normal tissue even if the tissue has high physiologic uptake	Target nodes/nodal masses must regress to ≤ 1.5 cm in LD _i No extralymphatic sites of disease
	Non measured lesion	Not applicable	Absent
	Organ enlargement	Not applicable	Regress to normal
	New lesions	None	None
	Bone marrow	No evidence of FDG-avid disease in marrow	Normal by morphology; if determinate, IHC negative
Partial	Lymph nodes and extralymphatic sites	Partial metabolic response	Partial remission (all of the following)

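### The Cohort 2A (DLBCL) entry rule admits nodes that already lie inside the nodal size limit for CT-based complete response

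*Protocol*

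**What the plan says.** Cohort 2A entry (Protocol Section 5.1) asks for "At least 1 measurable site of disease according to the Lugano Classification". The site must also be clearly measurable in two perpendicular dimensions and meet one of two size conditions joined by *or*:

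- "greater than 1.5 cm in the long axis regardless of short axis measurement"
- "greater than 1.0 cm in the short axis regardless of long axis measurement"

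The response table in Appendix 10 (Section 10.10.2) has a PET-CT column and a CT column. The CT column defines "Complete radiologic response (all of the following"). Its nodal condition is "Target nodes/nodal masses must regress to ≤ 1.5 cm in" longest diameter (LDi). The other conditions are no extralymphatic disease, no remaining non-measured lesions, normal organ size, no new lesions and normal marrow.

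Section 9.6.1 defines the DLBCL response rate as confirmed CR or PR under Lugano, and this is the Part 2 primary endpoint. Section 9.1.2 gives the benchmark: "All evaluations in Part 2 are designed to exclude a 10% response rate representing best available therapy", in favour of 30%. Section 9.2.2 declares a subgroup effective if the posterior probability that ORR exceeds 10% is above 85%.

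On imaging, Table 2 in Section 1.3 says "Must include CT Chest. Must include CT abdomen if history of documented intraabdominal disease". Section 8.1.2 refers lymphoma response to that table and to Appendix 10.

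**The concern.** The two size rules use different axes. Entry can rest on the short axis alone, while CT-based nodal CR looks only at the long axis. Where they overlap, the nodal size component of CR does not separate a node that shrank from one that never changed. A participant in the overlap could meet that component at baseline, at the week 9 scan and at the confirmatory scan at least 4 weeks later.

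Cohort 2A has no comparator. Its response rate is set against a fixed 10% in small MTAP subgroups, so a response credited without tumour shrinkage goes straight into the estimate, and nothing in the design would reveal it.

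**Working it through.** **1. Is the overlap real?** Write LDi for the long axis and SDi for the short axis, in cm.

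- Eligible (Section 5.1): LDi > 1.5 or SDi > 1.0.
- Inside the CT nodal CR limit (Section 10.10.2): LDi ≤ 1.5.
- Both together: 1.0 < SDi ≤ LDi ≤ 1.5.

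On a 0.1 cm grid, both axes run over the five values 1.1 to 1.5 with SDi ≤ LDi. That gives 5 x 6 / 2 = 15 size pairs, from 1.1 x 1.1 to 1.5 x 1.5. With the long-axis condition alone (LDi > 1.5) there are none, so the overlap comes entirely from the short-axis alternative.

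**2. Example.** A sole node of 1.4 x 1.2 cm is eligible because 1.2 > 1.0, and 1.4 ≤ 1.5 already. Its product is 1.4 x 1.2 = 1.68 cm². CT-based PR would need a fall of at least 50%, to 0.84 cm² or less. Unchanged, the node is nowhere near PR but satisfies the CR size limit.

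**3. What else has to hold for an unchanged node to count as CR?**

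- Every target node lies in the overlap, and there is no extralymphatic, non-measured, organ or marrow disease. Section 5.1 allows this because one site is enough.
- The CT column governs.
- The nodal condition is read as an end state, not as a required decrease.

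**4. Illustration of size.** Table 9 assumes a 50:50 MTAP split, so 36 / 2 = 18 per subgroup. Without borrowing or futility looks, and with a logit-normal prior of mean -2.2 and variance 6.9, P(ORR > 10%) is 0.757 at 3/18 and 0.912 at 4/18. Four responses is therefore the first count above 85%, and it remains so at prior variances of 13.8 and 47.6.

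This simplified rule comes close to the plan's own figures:

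| | Simplified rule (≥ 4 of 18) | Table 9 |
|---|---|---|
| True ORR 10% | 9.8% | 8.2–8.3% |
| True ORR 30% | 83.5% | 81.3–81.7% |

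Now let k of the 18 be counted as responders automatically, with a true ORR of 10% in the rest. The false-success chance is P(X ≥ 4 − k), with X binomial(18 − k, 0.1):

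- k = 0: P(X ≥ 4 of 18) = 9.8%
- k = 1: P(X ≥ 3 of 17) = 23.8%
- k = 2: P(X ≥ 2 of 16) = 48.5%

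Each such participant adds 1/18 = 5.6 percentage points to the observed rate.

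The same can be put as a share f of otherwise non-responders counted this way, so that the apparent rate is 0.1 + 0.9f. For f = 0, 2, 5 and 10% the false-success chance is 9.8, 15.5, 25.9 and 45.5%. The documents give neither k nor f; both are assumptions.

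**The case against.** Four points on the other side have weight.

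- **The verb.** The table says "Target nodes/nodal masses must regress to" the limit. A node that stays at 1.4 x 1.2 cm has not regressed, and it fits the CT definition of stable disease (less than a 50% fall, no progression). This is a natural reading. But no amount of decrease is stated and no baseline above 1.5 cm is required. The organ-enlargement row uses the same verb and must also cover participants whose organs were never enlarged, so an end-state reading is open too. Response is investigator-assessed (Section 4.1), so the ambiguity matters.
- **The column.** A reader might infer from Table 2 that the CT column applies at every visit. The documents do not say so. The CT wording is a minimum, and the amendment summary ties the chest CT to thromboembolic events. Appendix 10 has a full PET-CT column and uses PET-CT for extent of disease in avid lymphomas. In that column CR depends on uptake and a residual mass is allowed, so the size gap disappears. On the other side, the schedule names only CT, the modalities exemplified in Section 8.1 omit PET, and Section 4.1.1 leaves PET/CT to the committee's discretion for Part 1 PK/PD cohorts. The governing column is left open.
- **Progression.** A reader might also infer that such a node is too small ever to progress, since progression needs LDi above 1.5 cm. That does not follow, because the test applies to the node when progression is assessed. Growth from 1.4 x 1.2 to 2.0 x 1.3 cm gives LDi 2.0, a product of 2.60 against 1.68 (up 55%) and a long-axis increase of 0.6 cm, which meets the rule.
- **Rarity.** The scenario needs relapsed or refractory disease confined to small nodes, with every other CR condition met. That is probably uncommon. Section 5.1 also cites Lugano measurability; Appendix 10 gives no baseline size definition that would close the gap, and the source cannot be checked here.

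**Conclusion.** The size overlap follows directly from the two thresholds. A participant with nodal-only disease and every target node at 1.0 < SDi ≤ LDi ≤ 1.5 cm enters Cohort 2A already inside the CT nodal CR limit.

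The stronger statement, that such a participant would be scored a responder without any drug effect, does not follow from the text alone. It needs the CT column, an end-state reading of the nodal condition and fulfilment of all the other CR conditions. Where these hold, the bias in ORR is upward.

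Its size is not known. The rise from 9.8% to about 24% is conditional on one such participant among 18 and leaves out the borrowing and futility looks that the design uses. It shows sensitivity and is not an estimate.

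This is a flaw in the protocol's design text. No reported result changes, because SAP Section 2.1 states that Part 2 and its response-rate analysis will not be performed. It matters if the criterion is reused.

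**What to change.** Reconcile Section 5.1 with Appendix 10 in one of two ways:

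1. Require a qualifying nodal site to have a baseline LDi above 1.5 cm, which removes the short-axis-only alternative for nodes; or
2. Keep the entry rule and state in Appendix 10 that CT-based nodal CR requires a documented decrease from a baseline LDi above 1.5 cm.

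In either case, name the Lugano column that governs DLBCL response and make the imaging schedule match it.

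Leave the extranodal entry size as it is. CT-based CR already requires no extralymphatic disease, so the gap concerns nodes only. A long-axis rule of above 1.0 cm for extranodal sites would admit, for example, a 1.2 x 0.6 cm site that the present rule excludes.

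The cost is about one line of text plus the statement of the column. Under the first option a few patients whose only nodes measure 1.1 to 1.5 cm become ineligible. Under the second they stay eligible but cannot reach CT-based nodal CR.
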